2. Subjects who choose to discontinue pexidartinib treatment will be enrolled into the Treatment-Free period of the **Treatment-Free/Re-Treatment Cohort**. The assessments from the subject's End-of-Treatment visit from their prior study (eg, tumor assessments, PRO measures, and safety parameters) will serve as the Baseline measurements for PL3397-A-U4003 study. Subjects will discontinue pexidartinib treatment and undergo clinical assessments at 3-month intervals during the Treatment-Free period. Re-treatment with pexidartinib will be based on the discretion of the subject and Investigator. Tumor assessment, subjective and/or functional measures, and safety will be considered in the decision-making process. The rationale for discontinuing and restarting pexidartinib re-treatment will be recorded accordingly.

Subjects in the **Treatment-Free/Re-Treatment Cohort** who enter the Re-Treatment period will be administered pexidartinib at the dose at which they completed the prior study. Dosing is required on an empty stomach (at least

1 hour before or 2 hours after a meal or snack), at approximately the same times of the day, and approximately 12 hours apart. During the Re-Treatment period, Investigators will ensure weekly liver monitoring tests for the first 8 weeks (2 months), then every 2 weeks for 1 month, then once every 3 months or more frequently as directed by the Investigator.

The Investigator will evaluate the MRI scans every 6 months for subjects in the Treatment Continuation Cohort and every 3 months for subjects in the Treatment-Free/Re-Treatment Cohort to perform a qualitative tumor assessment (i.e., stable disease) for subjects in the Treatment Continuation Cohort. Additional imaging assessments may be performed with changes in tumor response(s) as deemed necessary by the Investigator.

Patient Reported Outcomes (PROs) measures will be performed at 3-month intervals for all subjects.

Ongoing safety assessment, laboratory assessments (serum chemistry and hematology), and physical examination will be performed at 3-month intervals and monitored for adverse events (AEs). Note that laboratory assessments for urinalysis will be performed at 6-month intervals.

See [Figure 1.1](#) for the study flow diagram.

Study Duration

The study start is the date when the first subject has signed the informed consent. Subjects will be evaluated for eligibility at the last visit of their prior study.

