3. OBJECTIVES, OUTCOME MEASURES, AND ENDPOINTS

The objectives, definitions of associated endpoints, as well as applicable outcome measures are described in [Table 3.1](#) and [Table 3.2](#). Further requirements for the endpoint analyses and censoring rules, where applicable, can be found in [Section 9.5.1](#), [Section 9.5.2](#), and [Section 9.5.3](#).

Table 3.1: Description of Objectives, Outcome Measures, and Endpoints (Treatment-Free/Re-Treatment Cohort)

Period	Objectives	Outcome Measure	Endpoints	Category
Primary Objective				
Overall	Proportion of subjects who remain treatment-free	
Title: Proportion of treatment-free subjects at 12 months and 24 months
 
Description: Proportion of subjects who remain treatment-free at Month 12 and Month 24
 
Time frame: 24 months after last subject enrolled in the Cohort
	Proportion of subjects who remain treatment-free at Month 12 and Month 24	Efficacy
Secondary Objectives				
Treatment-Free period	Change from Baseline in Patient Reported Outcomes (PROs)	
Title: Change from Baseline in PROs
 
Description: Change from Baseline in PROs (PROMIS PF, EQ-5D-5L)
 
Time frame: 24 months after last subject enrolled in the Cohort
	Mean change from Baseline* for PROMIS PF and EQ-5D-5L quarterly for the treatment-free and Re-Treatment periods. *Note: Baseline is Screening values.	Efficacy
	Safety	
Title: Number of subjects with AE during the Treatment-Free period*
 
Description: Total number of subjects in the safety analysis set with any AE collected between Screening and start of re-treatment or final database lock (whichever occurs first)
 
Time frame: 24 months after last subject enrolled in the Cohort
 
*Note: Listed as a secondary objective but is a primary outcome measure.
	Incidence of AEs and SAEs, ECGs, and laboratory assessments	Safety
Re-Treatment period	Tumor Assessment	
Title: Tumor assessment
 
Description: Investigator evaluation of tumor
 
Time frame: 24 months after last subject enrolled in the Cohort
	Qualitative assessment of the tumor	Efficacy

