	Change from Baseline in Patient Reported Outcomes (PROs)	
Title: Change from Baseline in PROs
 
Description: Change from Baseline in PROs (PROMIS PF, EQ-5D-5L)
 
Time frame: 24 months after last subject enrolled in the Cohort
	Mean change from Baseline* for PROMIS PF and EQ-5D-5L quarterly for the Re-Treatment periods. *Note: Baseline is reinitiated with subject entering Re-Treatment period.	Efficacy
	Safety	
Title: Number of subjects with AE during the Re-Treatment period*
	Incidence of TEAEs and SAEs, ECGs, and laboratory assessments	Safety

Period	Objectives	Outcome Measure	Endpoints	Category
		
Description: Total number of subjects in the safety analysis set with any AE collected between first re-treatment dose and final database lock
 
Time frame: 24 months after last subject enrolled in the Cohort
 
*Note: Listed as a secondary objective but is a primary outcome measure.
		

AE = adverse event; EQ-5D-5L = EuroQol-Five Dimension Five Level Scale; PRO = Patient-Reported Outcomes ; PROMIS PF = Patient-Reported Outcomes Measurement Information System – Physical Function; SAE = serious adverse event; TEAE = treatment-emergent adverse event

Table 3.2: Description of Objectives, Outcome Measures, and Endpoints (Treatment Continuation Cohort)

Objectives	Outcome Measure	Endpoints	Category
Primary Objective			
None			
Secondary Objectives			
Tumor Assessment	
Title: Tumor assessment
 
Description: Investigator evaluation of tumor
 
Time frame: 24 months after last subject enrolled in the Cohort
	Qualitative assessment of the tumor	Efficacy
Change from Baseline in PROs	
Title: Change from Baseline in PROs
 
Description: Change from Baseline in PROs (PROMIS PF, EQ-5D-5L)
 
Time frame: 24 months after last subject enrolled in the Cohort
	Mean change from Baseline* for PROMIS PF and EQ-5D-5L at quarterly assessments. 
*Note: Baseline is Screening values.
	Efficacy
Safety	
Title: Number of subjects with TEAE during the study*
 
Description: Total number of subjects in the safety analysis set with any AE collected between first dose and final database lock
 
Time frame: 24 months after last subject enrolled in the Cohort
 
*Note: Listed as a secondary objective but is a primary outcome measure.
	Incidence of TEAEs and SAEs, ECGs, and laboratory assessments	Safety

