3.1. Rationale for Selection of Primary and Key Secondary Endpoints

The primary and secondary endpoints were selected based on the clinical relevance and potential import for guiding the treatment of pexidartinib in patients with TGCT. Information on objective (tumor response), subjective (PROMIS-Physical Function Questionnaire, European Quality of Life Five Dimension Five Level Scale [EQ-5D-5L]), and safety measures for subjects with TGCT are all relevant for prescribers, patients, and regulators.

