For subjects who restart pexidartinib treatment in the Re-Treatment period of the **Treatment-Free/Re-Treatment Cohort**, pexidartinib will be administered at the dosage level at which the subject completed the prior study. Doses must be administered on an empty stomach (at least 1 hour before or 2 hours after a meal or snack), at approximately the same times of the day, and approximately 12 hours apart. The full set of study assessments will be performed (Baseline-2). During re-treatment, Investigators will ensure weekly liver monitoring tests for the first 8 weeks, then every 2 weeks for the next month, then every 3 months or more frequently as directed by the Investigator (see [Table 6.3](#)).

The Investigator will evaluate the quarterly magnetic resonance imaging (MRI) scans to perform a qualitative tumor assessment (i.e., stable disease) for subjects in the **Treatment-Free/Re-Treatment Cohort**. Additional assessments may be conducted based on worsening of tumor response as deemed necessary by the Investigator. For those subjects who restart pexidartinib treatment in the Re-Treatment period of the **Treatment-Free/Re-Treatment Cohort**, the response should note “Progression” and the assessments after re-treatment should use Baseline 2 as the reference to determine Progression or Non-Progression.

The PROs (PROMIS PF and EQ-5D-5L) will be performed every 3 months for all subjects.

Ongoing safety will include serum chemistry, hematology, urinalysis, coagulation, ECG, hormone testing, and physical examination, and subjects will be monitored for adverse events (AEs)/TEAEs.

Subjects on treatment who end their study participation early with no radiologic disease progression will undergo a final MRI 3 months \pm 14 days after their last dose of study treatment or before any new TGCT therapy, including surgery.

Subjects who discontinue early from the study will complete the End-of-Study (EOS)/EOT visit and will be withdrawn from the study.

The subject population is described in [Section 5](#). A flow diagram of the study is presented in [Figure 1.1](#).

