9.5.1.2. Secondary Efficacy Analyses

The PRO measures will be summarized descriptively over time along with its 95% CI by each cohort. The mean change from Baseline for these measures will also be reported over time along with its 95% CI by each cohort. The analysis will be conducted in the Evaluable Analysis Set (EAS).

Similar analyses will be conducted in the Re-treatment Analysis Set subjects (RAS). In this analysis, the Baseline measure of the retreated subjects is defined as the latest measure prior to or on the date of re-treatment of pexidartinib.

Qualitative assessments of the tumor will be summarized descriptively for pexidartinib re-treated subjects in the **Treatment-Free/Re-Treatment Cohort** and for all subjects in the **Treatment Continuation Cohort**.

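### The re-treatment PRO analysis takes its only reference from the score at restart, which may have helped prompt the restart, so its mean change is open to regression to the mean

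*Combined protocol and SAP*

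**What the plan says.** Section 9.5.1.2 plans two PRO analyses. The first is by cohort in the Evaluable Analysis Set (EAS): "The mean change from Baseline for these measures will also be reported over time along with its 95% CI by each cohort". The second repeats this in the Re-Treatment Analysis Set (RAS) with a new reference: "the Baseline measure of the retreated subjects is defined as the latest measure prior to or on the date of re-treatment of pexidartinib". The re-treatment row of Table 3.1 agrees: "Baseline is reinitiated with subject entering Re-Treatment period".

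The treatment-free row of Table 3.1 also reaches into re-treatment. Its endpoint is "Mean change from Baseline* for PROMIS PF and EQ-5D-5L quarterly for the treatment-free and Re-Treatment periods", with the note "Baseline is Screening values".

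On the restart decision, the synopsis says: "Tumor assessment, subjective and/or functional measures, and safety will be considered in the decision-making process". Section 4.1.1 says much the same, and Section 8.3.3 has re-treatment considered at every treatment-free visit. Section 3.1 shows which measures count as subjective: "subjective (PROMIS-Physical Function Questionnaire, European Quality of Life Five Dimension Five Level Scale [EQ-5D-5L". No PRO threshold for restarting is given. The reason for restarting is to be recorded (Sections 1.1 and 4.1.1). At restart, "The full set of study assessments will be performed (Baseline-2"), and Table 1.3 includes both questionnaires at that visit.

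The study has no randomization or blinding (Section 6.3), no hypothesis and no p-values (Section 9.1).

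**The concern.** A questionnaire score is a stable level plus visit-to-visit noise. If a low score helps to trigger a restart, subjects enter the RAS at visits where the noise tends to be negative. When that same score is the reference, the next score tends to be higher whatever the treatment does. The planned 95% CI describes sampling error around the mean change and makes no allowance for this selection.

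The stake is how the re-treatment result is read. Section 4.2 assumes that restarting will stabilize disease again, and Section 2.2 gives evidence on effective re-treatment as a purpose of the study. The other re-treatment efficacy outcome is a qualitative tumor assessment whose reference is also reset to Baseline-2 (Section 4.1.1; Table 1.3, footnote e). A positive PRO change with an interval above zero, and no control group, would readily be taken as benefit.

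**Working it through.** **Stated inputs.** The documents give no sample size, PRO standard deviation, reliability or expected change, so there is no planned figure to reproduce. All sizes below are illustrations in SD units on assumed inputs.

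**Step 1: closed form.** Take one visit at which the lowest-scoring fraction f restarts, with test-retest correlation ρ and no true change. The expected rebound is (1 − ρ) × φ(z_f) / f.

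- f = 20%: φ(z_f)/f = 1.40, giving 0.4 × 1.40 = +0.56 SD at ρ = 0.6 and 0.1 × 1.40 = +0.14 SD at ρ = 0.9.
- f = 50%: φ(z_f)/f = 0.798, giving +0.32 SD at ρ = 0.6 and +0.08 SD at ρ = 0.9.

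**Step 2: simulation of quarterly visits.** Score = T + e, with Var(T) = ρ and Var(e) = 1 − ρ. There is no drug effect and no true change. In a given share of subjects, restart is PRO-driven: it occurs at the first of seven quarterly visits with a fall from Screening of more than 0.5 SD. The others restart with probability 0.08 per visit, unrelated to the score. Follow-up is three months later. With the triggering score as baseline and independent noise:

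| PRO-driven share of subjects | Change from restart score, ρ = 0.6 / 0.7 / 0.8 / 0.9 | Change from Screening, same subjects |
|---|---|---|
| 100% | +0.687 / +0.621 / +0.543 / +0.444 | −0.284 / −0.272 / −0.260 / −0.248 |
| 50% | +0.415 / +0.369 / +0.305 / +0.215 | −0.175 / −0.161 / −0.146 / −0.122 |
| 25% | +0.231 / +0.204 / +0.168 / +0.104 | −0.095 / −0.088 / −0.078 / −0.063 |
| 0% | about 0 | about 0 |

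The share refers to all subjects, not to restarts. At ρ = 0.7, 64% of PRO-driven and 44% of other subjects restart. A 50% share therefore makes 0.32 / (0.32 + 0.22) = 59% of restarts PRO-driven, and 0.59 × 0.621 = 0.37 agrees with the table.

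**Step 3: effect on the interval.** The chance that the 95% CI lies wholly above zero is Φ(m / (s/√n) − 1.96). At ρ = 0.7 and a 50% share, m = 0.369 and s = 0.79. With n = 10 re-treated subjects, 0.369 / (0.79/√10) = 1.48, and Φ(1.48 − 1.96) is about 0.31. Over ρ = 0.6 to 0.9 the chance is 17–18% for n = 5, 30–32% for n = 10 and 52–56% for n = 20, against a nominal 2.5%.

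**Step 4: what shrinks it.**

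- Fresh Baseline-2 score with independent noise: about 0 in every setting.
- Noise correlated 0.5 between quarters (ρ = 0.7, 50% share): +0.14 SD with the triggering score, +0.12 SD with a fresh score about two weeks later.
- True untreated worsening over the three months after restart: about 0.2 to 0.4 SD cancels the artefact at a 50% share. At ρ = 0.9, worsening of 0.3 SD turns +0.215 into −0.083.

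**Step 5: does the plan already supply the second reference?** Table 3.1 names a Screening-anchored change covering the re-treatment periods. Section 9.5.1.2 carries Screening only into the by-cohort EAS mean. At a given study quarter, that mean can mix re-treated subjects with those still off treatment. For the RAS, the only reference stated is the restart score.

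**The case against.** Four points on the other side carry weight.

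- **A Screening anchor exists.** Since only re-treated subjects have re-treatment data, the treatment-free row of Table 3.1 can be taken to specify it for them already. A reader might infer that the plan never measures re-treatment PROs from any other reference; Table 3.1 contradicts that. What stands is that Section 9.5.1.2 does not carry this anchor into the RAS.
- **Restart need not depend on PROs.** Tumor assessment and safety also count. Section 4.2 expects suspension to last until signs of progression, and Section 4.1.1 has progression noted for those who restart. Restarts resting on MRI or safety alone carry little or no such bias. A reader might infer that the PRO score was the reason for each restart, or that the mean change is bound to show improvement. The documents support neither.
- **Baseline-2 is its own assessment.** The latest-measure rule already prefers it to an earlier triggering score. This largely answers the concern if the scores are separate and the noise independent. The protocol does not say that the two visits must differ.
- **The endpoint is secondary and descriptive.** That limits the consequences but does not correct the reading of an interval above zero. Section 9.5 also defers detail to a SAP, so the point concerns Section 9.5.1.2 as it stands.

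Two further inferences fail. The PROs are not the only functional information on re-treatment, because physical examinations in Table 1.3 include function of the affected joint. Nor do the two references necessarily enclose the true effect. In the 50%, ρ = 0.9 case with 0.3 SD of untreated worsening and no drug effect, change from restart is −0.083 and change from Screening is −0.122 − 0.3 = −0.42, so both lie below zero.

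**Conclusion.** The point holds as a vulnerability of one analysis. The RAS mean change is referred only to a score that may have contributed to selection, and no second reference, split by restart reason or caution is stated for it. The artefact could be anywhere from 0 to about +0.7 SD, depending on how many restarts are PRO-driven, the reliability of the scores, and whether Baseline-2 is a separate measurement. Those inputs are assumed, and real deterioration off treatment could hide the artefact altogether.

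The Screening reference gave no false improvement in the zero-effect, zero-change simulations, but it is not neutral: it leans towards decline and carries any earlier real loss. Each reference answers a different question, and neither alone isolates a drug effect. A secondary issue follows: Table 3.1 uses two baselines for re-treatment visits, and Section 9.5.1.2 does not say which one serves those visits in the EAS analysis.

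**What to change.** Amend Section 9.5.1.2, and carry the change into the SAP before database lock, as follows:

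1. For the same RAS subjects at each re-treatment visit, report PROMIS PF and EQ-5D-5L against both references: change from Baseline-2, and change from the original on-drug (Screening) Baseline. The second shows whether function has returned to its level before discontinuation.
2. Show both by recorded restart rationale where numbers allow.
3. State which baseline applies to re-treatment visits in the by-cohort EAS analysis, so that it agrees with Table 3.1.
4. State that change from Baseline-2 alone is open to selection and is not to be read as a drug effect.

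The cost is revised wording and one extra table. The questionnaires and the restart rationale are already collected, and no visit or procedure changes. The sponsor should accept that the headline improvement may look smaller.

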9.5.1.3. Exploratory Analyses

Exploratory analysis will be descriptive only. Details of the exploratory analysis will be specified in the SAP.

9.5.1.4. Multiplicity Adjustment

Not applicable.

9.5.2. Safety Analyses

Safety analyses will be performed using the Safety Analysis Set and subjects will be analyzed by cohort separately.

Adverse Events

TEAEs are defined as new AEs or pre-existing conditions that worsen in CTCAE grade after the first dose of study drug and up to 30 days after last dose of study drug. AEs collected after 30 days after the last dose of study drug will not be considered TEAEs unless they are treatment related. AEs will be coded using the Medical Dictionary for Regulatory Activities (MedDRA) dictionary. An AE will be assigned to the study period in which it started, even if it resolved in a subsequent period. Incidence of TEAEs occurring over time, (e.g., 0 to 6 months, 6 to 12 months, etc.) will be summarized. The number and percentage of subjects reporting TEAEs will be calculated overall, by system organ class, by preferred term, and by cohort.

TEAEs will be further summarized by CTCAE grade and relationship to study drug. Similarly, the number and percentage of subjects reporting treatment-emergent SAEs and related treatment-emergent SAEs will be tabulated, and TEAEs leading to discontinuation of study drug.

A by-subject AE (including treatment-emergent) data listing including but not limited to verbatim term, preferred term, system organ class, CTCAE grade, and relationship to study drug will be provided. Deaths, other SAEs, AESIs, and AEs associated with study drug discontinuation, will be listed. AEs due to COVID-19 will be also summarized and listed.

Clinical Laboratory Evaluation

Descriptive statistics will be provided for the clinical laboratory results by scheduled time of evaluation and by cohort, as well as for the change from Baseline. The Baseline value is defined as the last non-missing value before the initial administration of study drug. In addition, mean change from Baseline will be presented for the maximum and minimum post-treatment values and the values at the EOT visit.

Abnormal clinical laboratory results will be graded according to NCI-CTCAE version 5.0, if applicable, and the grade will be presented in a by-subject data listing. A shift table, presenting by cohort the two-way frequency tabulation for baseline and the worst post-treatment value according to the CTCAE grade, will be provided for clinical laboratory tests. A listing of abnormal clinical laboratory test results deemed of clinical significance or of Grade 3 or 4 will be generated.

ECG

Descriptive statistics will be provided for the ECG measurements by scheduled time of evaluation and by cohort, as well as for the change from Baseline. The Baseline value is defined as the last non-missing value before the initial administration of study treatment. A listing of ECG data will be generated.

Vital Signs

Descriptive statistics will be provided for the vital sign measurements by scheduled time of evaluation and by cohort, as well as for the change from Baseline. The Baseline value is defined as the last non-missing value before the initial administration of study treatment. A listing of vital sign data will be generated.

Other

Listings of all other safety endpoints (e.g., physical examination findings) will be generated.

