4.1.4. Duration

The study start date is the date when the first subject signs the ICF and the study continues until the last subject has had their last visit.

Duration of Treatment and Subject Participation

Subjects will be evaluated for eligibility at the last visit of their prior study.

Subject in the **Treatment Continuation Cohort** will undergo study assessments at 3-month intervals for a maximum of 24 months.

Subjects in the **Treatment-Free period of the Treatment-Free/Re-Treatment Cohort** will undergo study assessments at 1 month after enrollment, 3 months after enrollment, and then at 3-month intervals until either re-treatment with pexidartinib or for a maximum of 24 months.

Subjects in the **Re-Treatment period of the Treatment-Free/Re-Treatment Cohort** will undergo study assessments at M1, M2 and then at 3-month intervals. The maximum duration for any subject within the combined periods of the **Treatment-Free/Re-Treatment Cohort** is 24 months. Liver safety assessments will follow a separate schedule (See [Table 1.3](#)).

The study will end with the last subject's last visit. A post-trial access plan, delineating options for access to pexidartinib, will be available for subjects after completing their study participation if the subject is benefiting from the study drug.

Overall Study Duration

Anticipated total duration of the study is expected to be approximately 24 months. See Section [4.1](#) for the definition of study start and Section [4.1.2](#) for the definition of the overall EOS.

Study Drug Continuation After the End of Study

A post-trial access plan, delineating options for access to pexidartinib, will be available for subjects after completing their study participation if the subject is benefiting from the study drug.

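### Adverse-event counts and percentages cover Treatment-Free and Re-Treatment periods of unequal length with no time-at-risk measure, so off-drug and on-drug figures set side by side can be distorted by time observed

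*Combined protocol and SAP*

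**What the plan says.** Section 9.5.2 sets the AE summary: "The number and percentage of subjects reporting TEAEs will be calculated overall, by system organ class, by preferred term, and by cohort". It adds a summary by interval, "Incidence of TEAEs occurring over time, (e.g., 0 to 6 months, 6 to 12 months, etc.) will be summarized", without a time origin or a denominator. Events are allocated by onset: "An AE will be assigned to the study period in which it started, even if it resolved in a subsequent period".

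Table 3.1 and the synopsis define two period-level AE outcomes for the Treatment-Free/Re-Treatment Cohort:

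- Treatment-Free: "Total number of subjects in the safety analysis set with any AE collected between Screening and start of re-treatment or final database lock", whichever is earlier.
- Re-Treatment: subjects with "any AE collected between first re-treatment dose and final database lock".

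Notes to both rows say that, although listed under secondary objectives, they are primary outcome measures.

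On period length, Section 4.1.1 leaves restart to the discretion of investigator and subject. Section 4.1.4 fixes the overall limit: "The maximum duration for any subject within the combined periods of the" Treatment-Free/Re-Treatment Cohort is 24 months. The Treatment Continuation Cohort also runs to a maximum of 24 months.

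On carry-over, Section 9.5.2 defines treatment-emergent AEs (TEAEs) as those arising or worsening "after the first dose of study drug and up to 30 days after last dose of study drug". Section 4.1.1 places the last dose of a Treatment-Free subject at the final visit of the prior study.

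Section 9.1 calls the analysis descriptive, with no hypothesis. Section 9.5 describes itself as a summary ahead of an SAP, and Section 9.5.3 plans no other analyses.

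**The concern.** The proportion of subjects with at least one AE rises with the time they are watched. Here the time is not common to the two periods. A subject who restarts at month s contributes s months off drug and at most 24 − s months on re-treatment, and s is chosen case by case. A subject who never restarts has no second period. Crude counts therefore mix risk with length of observation.

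Section 2.2 says the study is meant to inform whether stopping and restarting the drug is safe and works. Readers will set the off-drug AE figure beside the re-treatment figure, and beside the Continuation Cohort. With equal risk, the period watched longer shows the higher percentage. With unequal risk, the percentages can hide or reverse the difference.

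The interval summary does not clearly repair this. It covers TEAEs, whereas the Treatment-Free outcome is AEs, and its origin and denominator are not stated.

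**Working it through.** The documents give no AE rate, restart rate or sample size, so there is no stated figure to reproduce. What follows is illustrative.

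**Inputs.** From Section 4.1.4: 24 months shared by the two periods, and up to 24 months in the Continuation Cohort. From Table 1.2: a month is 30 days. Assumed: a constant first-AE rate λ per subject-month, with a range shown. Percentages are of subjects who enter the period.

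**1. Equal risk on and off drug.** P(at least one AE in T months) = 1 − exp(−λT), with T = s off drug and 24 − s on re-treatment.

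| Restart at month | λ | Treatment-Free | Re-Treatment |
|---|---|---|---|
| 3 | 0.02 | 5.8% | 34.3% |
| 3 | 0.05 | 13.9% | 65.0% |
| 3 | 0.10 | 25.9% | 87.8% |
| 6 | 0.05 | 25.9% | 59.3% |
| 12 | 0.05 | 45.1% | 45.1% |
| 18 | 0.02 | 30.2% | 11.3% |
| 18 | 0.05 | 59.3% | 25.9% |
| 18 | 0.10 | 83.5% | 45.1% |

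For example, 1 − exp(−0.05 × 18) = 59.3% and 1 − exp(−0.05 × 6) = 25.9%. The direction depends on when restart occurs, and at month 12 the gap is zero.

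**2. Risk doubled on drug.** Take 0.05 off drug and 0.10 on drug, with restart at month 18. Off drug: 1 − exp(−0.05 × 18) = 59.3%. On re-treatment: 1 − exp(−0.10 × 6) = 45.1%. The riskier period shows the lower percentage.

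**3. Treatment-Free period against the Continuation Cohort, equal risk.** Let p be the assumed share still treatment-free at month 12, and h = −ln(p)/12 a constant restart rate. Then P(AE while treatment-free) = λ/(λ + h) × [1 − exp(−24(λ + h))], against 1 − exp(−24λ) in the Continuation Cohort. At λ = 0.05 the Continuation figure is 69.9%:

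- p = 90%: h = 0.00878, giving 64.3%, a gap of 5.6 points.
- p = 70%: 53.5%, a gap of 16.4 points.
- p = 50%: 42.9%, a gap of 27.0 points.

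At p = 90%, λ = 0.02 gives 34.7% against 38.1%, and λ = 0.10 gives 85.2% against 90.9%. The gap there is about 3 to 6 points.

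**4. Front-loaded risk.** Section 2.1.2 says the hepatic reactions appear mostly in the first 8 weeks of treatment. Assume 0.10 per month for 2 months, then 0.01.

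- Over 6 months: 1 − exp(−0.24) = 21%. Over 18 months: 1 − exp(−0.36) = 30%. The gap is 9 points.
- Mean time at risk to first AE is (1 − e^−0.2)/0.10 + e^−0.2 × (1 − e^−0.04)/0.01 = 5.02 months over the 6-month period. With e^−0.16 in place of e^−0.04 it is 13.92 months over the 18-month period.
- Rates per 100 subject-years: 0.2134/5.02 × 1200 ≈ 51, and 0.3023/13.92 × 1200 ≈ 26.

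The risk profile is the same in both periods, yet the subject-year rate differs about twofold, and in the opposite direction to the crude percentages.

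**5. The first 30 days off drug.** Their share of a Treatment-Free period of T months is 1/T: 33.3% of 3 months, 16.7% of 6, 8.3% of 12 and 4.2% of 24. If the AE rate in those days is twice the later rate (assumed), they hold 2/(T + 1) of expected AEs: 50.0%, 28.6%, 15.4% and 8.0%.

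**The case against.** The strongest reply has four parts.

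- **No comparison is planned.** The primary objective is the proportion remaining treatment-free, and the study is descriptive. That is so. But with no tests, these counts are the safety evidence, and the plan itself labels them primary outcome measures.
- **The illustration is selective.** A reader might infer from 59% against 26% that the AE results mainly reflect time observed. The documents do not support that. It depends on rates they do not give, on an assumed constant hazard and on one restart time. Restart at month 12 gives no gap, front-loaded risk shrinks the gap to 9 points, and high retention off drug leaves about 3 to 6 points against the Continuation Cohort. This part stands.
- **A rate per subject-year is no cure.** Step 4 shows that it can mislead as much as the crude percentage. This also stands, and it changes the remedy.
- **Detail is deferred to the SAP, and intervals are already planned.** This stands in part. An unstated denominator is not a wrong one. Yet nothing in Section 9.5 points to a time-at-risk measure, and the interval summary is written for TEAEs only.

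A reader might also infer that the plan contradicts itself by counting the first 30 off-drug days as treatment-free. The text is ambiguous rather than contradictory. The TEAE window is tied to study drug, and it does not say whether it reaches back to the last dose in the prior study. The Treatment-Free outcome counts AEs, not TEAEs, and counting early events after stopping is defensible in a discontinuation study.

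**Conclusion.** The point holds as a weakness in reporting and interpretation. No figure in the plan is wrong. Followed as written, Section 9.5.2 and Table 3.1 give AE counts and percentages over periods whose lengths vary by subject and share 24 months, with nothing to separate risk from time observed. The distortion could run from none to large in either direction. At a constant 0.05 per month it is 33.4 points (59.3% against 25.9%) for restart at month 18, −51.1 points (13.9% against 65.0%) for restart at month 3, and zero at month 12. These sizes rest on assumed rates and cannot be narrowed from the documents.

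The 30-day issue is secondary. It is small for long treatment-free periods and matters mainly for early restarts. What it needs is clarification.

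**What to change.** Amend Section 9.5.2, or carry this into the SAP before it is finalised:

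1. Beside the counts, report for each period the cumulative incidence of first AE at common times from that period's start, for example 3, 6 and 12 months, censoring at period end. Alternatively, give interval summaries with a stated origin and with subjects still at risk in the interval as denominator. Apply this to Treatment-Free AEs as well as TEAEs.
2. Add subject-years and first-event rates per 100 subject-years, with a note that such a rate assumes roughly constant risk and can mislead when risk is front-loaded.
3. Show Treatment-Free AEs with onset within 30 days of the last prior-study dose separately from later ones, and state how the TEAE definition treats them.
4. Reconcile AE collection. Section 8.4.1 closes recording of non-serious AEs 30 days after the last dose, which read literally would end it early in the Treatment-Free period. Table 3.1 counts AEs throughout that period, and Table 1.2 has AE and diary rows across it. Without this the new figures would be incomplete.

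The cost is a few more table columns, built from AE onset and period dates, and slightly longer output. Late estimates will be sparse. Because Section 4.1.1 lets safety inform the restart decision, censoring at restart is itself an assumption and should be stated as one.
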